to the HB-adMSCs and Placebo groups, respectively. Safety assessments will be ongoing. Complete Blood Count, Comprehensive Metabolic Profile and Coagulation Panel will screen for hepatotoxicity, renal failure or alterations in the coagulation cascade that might entail a safety concern for the individual. Efficacy assessments will include PHQ-9, SF-36, TNF-a, IL-6, IL-10, and CRP.

The trial is designed to be conducted over 3 periods or phases:

- **Phase 1** (screening): Our screening process starts with a telephone call to provide a general overview of the study and discuss eligibility requirements. The study patient will receive the informed consent document by e-mail or in the pre-paid envelope provided. If, after reviewing this consent the study patient is still interested in participating in the study, he/she will need to sign and return the consent form to Hope Biosciences Stem Cell Research Foundation. This process can take up to 45 days.
- **Phase 2** (Treatments): Includes Infusion 1 (Week 0), Infusion 2 (Week 2), Infusion 3 (Week 6), Infusion 4 (Week 10) and Infusion 5 (Week 14). Subjects will be monitored at the clinical site for 1 hours following HB-adMSCs administration.
- **Phase 3** (follow-up): Includes Follow Up Week 18, 22 and End of Study at Week 26.

Selection and Withdrawal of Patients

Inclusion Criteria

Inclusion Criteria:

1. Men, and women 18 years of age or older
2. Participant works in a capacity that is characterized as high-risk or very high-risk
 - a. High-Risk Exposure jobs are those with high potential for exposure to known or suspected sources of COVID-19.
 - First responders, health care delivery and support staff (e.g., law enforcement, fire fighters, paramedics, doctors, nurses, and other hospital staff who must enter patients' rooms) exposed to individuals potentially having COVID-19.
 - Mortuary workers involved in preparing (e.g., for burial or cremation) the bodies of people who are known to have, or suspected of having, COVID-19 at the time of their death
 - b. Very High-Risk Exposure jobs are those with high potential for exposure to known or suspected sources of COVID-19 during specific medical, postmortem or laboratory procedures.
 - Health care workers (e.g., doctors, nurses, dentists, paramedics, emergency medical technicians) performing aerosol-generating procedures (e.g., intubation, cough induction

Allogeneic HB-adMSCs to provide immune support against COVID-19.

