Allogeneic HB-adMSCs to provide immune support against COVID-19.

Details of the investigational product

Allogeneic HB-adMSCs is to be administered as an IV infusion with a syringe containing 5×10^7 cells. Each syringe will be provided by Hope Biosciences on the day of the infusion after all quality control assays have been performed and the results are within normal range.

Instructions for Administration

The designated study staff will administer the investigational product in the following manner:

- Prior to administration, visually inspect the infusion solution for particulates. If foreign particles are present, do not use the solution.
- Emergency equipment, such as epinephrine, antihistamines, and corticosteroids must be available in the event of infusion-related reactions.
- Start IV administration after dilution.
- Administer the infusion solution over a period of 1h. Observe the patient for at least 2 hours post-infusion for acute infusion-related reactions, including anaphylaxis. See Appendix 1 for guidelines on diagnosing anaphylaxis.
- Do not store or reuse any unused portion of the infusion solution. Any unused product or waste material should be disposed.
- Volume of study drug infused, start times, and stop times will be recorded. If any portion of the infusion (cell solution) is discarded, the reason will be recorded in the CRF.
- The patient will be monitored for a total of 3 hours from drug exposure to discharge.
 - a. During the Investigational product administration (1 hour) vital signs will be measured at minute 0, 15, 30 and 45.
 - b. Post infusion, vital signs will be measured at minute 0, 30 and 60.

Investigational Product Assignment and Infusion Schedule (Randomization and Staggering)

Randomization

A total of 53 eligible subjects will be randomized to either placebo or treatment group within the associated study arm at baseline. Randomization will determine whether the subject receives placebo or HB-adMSCs.

A neutral, third-party personnel will be responsible for assigning the participants' treatment group. This role will be referred to as 'randomizer'. The designated personnel from the drug manufacturer will be responsible in labeling and packaging the investigational product for each participant. This role will be referred to as 'mixer'. Participants' names are not disclosed to the mixer and the unblinded information will only be known to the randomizer.

Staggering

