The PHQ-9 is the depression module, which scores each of the nine DSM-IV criteria as "0" (not at all) to "3" (nearly every day). It is not a screening tool for depression, but it is used to monitor

Allogeneic HB-adMSCs to provide immune support against COVID-19.

the severity of depression. In addition to making criteria-based diagnoses of depressive disorders, the PHQ-9 is also a reliable and valid measure of depression severity.

TNF- α

The primary role of TNF is in the regulation of immune cells. TNF, being an endogenous pyrogen, is able to induce fever, apoptotic cell death, cachexia, inflammation and to inhibit tumorigenesis and viral replication and respond to sepsis via IL1- & IL6-producing cells.

IL-10

IL-10 is a cytokine with multiple effects in immunoregulation and inflammation. It downregulates the expression of Th1 cytokines, MHC class II antigens, and co-stimulatory molecules on macrophages. It also enhances B cell survival, proliferation, and antibody production.

IL-6

Interleukin 6 (IL-6) is an interleukin that acts as both a pro-inflammatory cytokine and an antiinflammatory myokine. In humans, it is encoded by the *IL6* gene.

Safety Assessments

Safety assessments (vital signs, weight, physical examinations, AEs, routine clinical laboratory tests (CBC, CMP, PT and PTT/INR) will be performed at the visits specified in the schedule of assessments in Table 2.

Vital Signs, Height, and Weight

Vital signs (body temperature, pulse, oxygen saturation, systolic and diastolic blood pressure measurements) will be evaluated at the visits indicated in the schedule of assessments. It is important that all vital signs be measured after the patient has been resting in a sitting position for at least 5 minutes. Blood pressure measurements are to be taken in the same arm for the duration of the study. Body weight (without coats and shoes) will be recorded whenever vital signs are recorded, and height (without shoes) will be recorded at Infusion 1 (baseline) only.

Vital sign measurements will be repeated if clinically significant or machine/equipment errors occur. Out-of-range blood pressure and pulse measurements will be repeated at the Investigator's discretion. Any confirmed, clinically significant vital sign measurements will be recorded as AEs and followed up as such.

Physical Examination

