It is the responsibility of the Principal Investigator to oversee the safety of the study at his/her site. This safety monitoring will include careful assessment and appropriate reporting of adverse events as noted above. At Hope Biosciences, [name], MD [contact] will be responsible for reviewing any reported AEs and SAEs to determine if changes to the study need to be made or if the study should be stopped for the protection of patients. DSMB will review all deaths (to assure non-attribution), cases of anaphylaxis or suspected anaphylaxis, thromboembolic events, new malignancy/tumor, infections/hospitalizations (including unrelated to COVID-19 but due to underlying condition). After 15 subjects diagnosed with COVID-19, 5 subjects are hospitalized, or 3 subjects in the ICU, DSMB will review. DSMB will also review safety data at mid-point of the study.

Risks

Potential Risks of the Investigational Product and Clinical Investigation

Risks Associated with HB-adMSCs

Respiratory Risks:

A potential risk is that the infusion could initiate a VTE event with subsequent cardiopulmonary sequelae of respiratory failure and/or right heart strain/failure. We plan to monitor oxygen saturation, and respiratory rate/work of breathing for the first 2 hours post- infusion. The patient will be examined for VTE events (clinical exam, oxygen saturation) during each infusion visit and at each follow-up visit.

Hepatic Risks:

The reticuloendothelial system can sequester immature blood elements, theoretically resulting in hepatic injury. An acute elevation of the AST/ALT hepatic enzymes > 900 U/dl post-infusions will be considered an infusion related adverse event. This level is based upon the organ system scoring definitions for moderate hepatic failure and corresponds to the CTCAE v4.03 Grade 4 adverse event. It is unlikely that "end vessel" micro-thrombosis would occur in the liver due to the dual blood supply of the liver and the lung is the first pass organ. A CMP will be obtained at follow-up visits.

Coagulation Cascade:

A coagulation panel will be obtained at screening, baseline, infusion and the follow-up visits. The patient will be monitored for the development of venous thromboembolic events (see pulmonary monitoring above) as well as for the development of clinical deep vein thrombosis (limb swelling, tenderness, discoloration).

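### The two-hour respiratory monitoring named as the safeguard against infusion-related VTE is only partly carried into the protocol's operative sections

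*Protocol*

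**What the plan says.** The Protocol's Respiratory Risks paragraph names infusion-initiated VTE, with respiratory failure or right heart strain, as a potential risk. Its answer is: "We plan to monitor oxygen saturation, and respiratory rate/work of breathing for the first 2 hours" after the infusion. The Coagulation Cascade paragraph refers back to the same monitoring as part of its own VTE surveillance.

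Four other parts of the Protocol govern what staff actually do:

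- **Instructions for Administration** sets the duration: "Observe the patient for at least 2 hours post-infusion for acute infusion-related reactions", and "The patient will be monitored for a total of 3 hours from drug exposure to discharge". It also sets the timed readings after the infusion: "Post infusion, vital signs will be measured at minute 0, 30 and 60".
- **Vital Signs, Height, and Weight** defines the set as "body temperature, pulse, oxygen saturation, systolic and diastolic blood pressure measurements". Respiratory rate is not in it.
- **Investigational Plan**, treatment phase: "Subjects will be monitored at the clinical site for 1 hours following HB-adMSCs administration".
- **Assessments by Week, Infusion Visits** asks for a minimum of one hour of observation for infusion and allergic reactions, and points to the schedule of assessments for details. That schedule (Table 2) has one untimed vital-signs row and no row for post-infusion observation or respiratory rate.

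**The concern.** The risk section makes a specific commitment: two measures, over two hours, against a named hazard. A commitment of this kind protects participants only if the sections that staff work from repeat it. Here the stated observation time depends on which section is read, one of the two measures has no scheduled reading, and the other has none in the second half of the window.

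Staff working from the Investigational Plan would end the stated VTE safeguard an hour early. Staff who follow Instructions for Administration in full would keep the participant for two hours, but with no scheduled oximetry after 60 minutes and no prompt to count respirations at any time. One of the Study Stopping Rules is triggered by sustained infusion-related hypoxia (SaO₂ below 80% for over one minute). An episode in the second hour is less likely to be recorded if no saturation reading is due then.

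**Working it through.** No sample-size or error-rate calculation applies. The check sets the sections side by side and adds up times and readings.

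**Inputs (all from the Protocol)**

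| Item | Value | Section |
|---|---|---|
| Respiratory monitoring window | 120 min after infusion | Respiratory Risks |
| Infusion length | 1 h | Instructions for Administration |
| Observation after infusion | at least 2 h | Instructions for Administration |
| Exposure to discharge | 3 h | Instructions for Administration |
| Readings during infusion | 0, 15, 30, 45 min | Instructions for Administration |
| Readings after infusion | 0, 30, 60 min | Instructions for Administration |
| On-site monitoring after infusion | 1 h | Investigational Plan |
| Observation after infusion | at least 1 h | Infusion Visits |
| Infusions | 5 (Weeks 0, 2, 6, 10, 14) | Investigational Plan |
| Participants | 53 | Determination of Sample Size |

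**Step 1: duration.** Reproducing the Protocol's own figure: 1 h infusion + 2 h observation = 3 h, so Instructions for Administration is internally consistent and agrees with Respiratory Risks. Under the Investigational Plan the total is 1 h + 1 h = 2 h. The difference is 3 − 2 = 1 h at each of 5 infusions. The Infusion Visits text is a floor, so two hours satisfies it. It is a lower minimum for the same observation, not a contradiction.

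**Step 2: content of the readings.** Timed sets per infusion: 4 during + 3 after = 7. Taking these to be the vital signs as the Protocol defines them, 7 of 7 include oxygen saturation and 0 of 7 include respiratory rate. Respiratory rate is named nowhere in the Protocol except in Respiratory Risks.

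**Step 3: coverage of the window.** The last timed reading is at 60 min and the window runs to 120 min. Sets in minutes 61 to 120: 0. Uncovered share: (120 − 60)/120 = one half. Readings are 15 min apart during the infusion and 30 min apart in the first hour after it; the second hour has none.

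**Step 4: size of the remedy.** One added reading × 5 infusions = 5 per participant. Upper bound: 5 × 53 = 265, reached only if every participant receives all five infusions.

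**The case against.** The best defence is that the detailed instruction governs. Instructions for Administration requires two hours and agrees with the risk section; the Investigational Plan line is a one-sentence overview of the treatment phase; and the Infusion Visits list is introduced as general. On this view only the overview line is wrong. Much of this stands for duration, although the Protocol states no order of precedence and Table 2 does not settle the matter.

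A second defence is that Respiratory Risks promises monitoring without fixing a frequency, and that work of breathing can be judged by watching the participant. So no timed second-hour reading was promised, and the risk section is itself current text. This is fair as far as it goes: the absence of a 120-minute reading is an omission, not a contradiction. But watching cannot replace a measured oxygen saturation, and no section turns the promised respiratory rate into a scheduled step.

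Third, other safeguards remain: "The patient will be examined for VTE events (clinical exam, oxygen saturation) during each infusion visit and at each follow-up visit"; symptom-driven examinations; the telephone call 24 hours after each infusion; and investigator discretion to stop. These limit the consequence. None supplies a respiratory rate or a timed second-hour reading.

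A reader might also infer more than the documents support:

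- *That different sites would follow different rules.* This is a single-center trial. The risk is that the same staff rely on different sections.
- *That the Infusion Visits minimum permits discharge at one hour.* Instructions for Administration separately requires two.
- *That the one-hour text is the one in use.* Nothing in the documents shows which text staff follow.

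**Conclusion.** The point holds as a minor safety-procedure inconsistency. There is one direct conflict (one hour on site in the Investigational Plan against two hours elsewhere), one lower minimum for the same observation (Infusion Visits), one measure missing from the defined set (respiratory rate, 0 of 7 readings), and no scheduled oxygen-saturation reading in the second of the two promised hours.

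Two assumptions matter. The count of 0 of 7 assumes that the readings around the infusion use the Protocol's own definition of vital signs; Instructions for Administration gives no other list. The one-hour difference arises only if staff follow the Investigational Plan line. If they follow Instructions for Administration, the duration gap disappears, but the missing respiratory rate and the unmeasured second hour remain.

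Sample size, error rates and the efficacy analyses are untouched.

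**What to change.** Three wording changes to the Protocol:

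1. In the Investigational Plan (treatment phase) and in Infusion Visits, replace one hour with at least two hours after infusion.
2. Add respiratory rate to the defined vital signs, so that it is taken at each reading listed in Instructions for Administration.
3. In Instructions for Administration, add a reading at 120 minutes after infusion, before discharge, that includes oxygen saturation and respiratory rate.

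The cost is one extra reading per infusion (5 per participant, at most 265 in total), plus a respiratory-rate entry on the case report form if it lacks one; the form is not among the documents. The added reading falls within observation time that Instructions for Administration already requires, so no new visit is needed. If staff have been working to the one-hour text, participants would stay up to one hour longer at each infusion.

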Appendix 1: Clinical Criteria for Diagnosing Anaphylaxis

Anaphylaxis is defined as a serious allergic reaction that is rapid in onset and may cause death. The following criteria were outlined by Sampson et al from the Second Symposium on the Definition and Management of Anaphylaxis (a 2005 meeting of the National Institute of Allergy and Infectious Disease and Food Allergy and Anaphylaxis Network).

Anaphylaxis is highly likely when any 1 of the following 3 criteria are met:

1. Acute onset of an illness (minutes to several hours) with involvement of the skin, mucosal tissue, or both (e.g., generalized hives, pruritus or flushing, swollen lips-tongue-uvula) AND at least 1 of the following:
 - a. Respiratory compromise (e.g., dyspnea, wheeze-bronchospasm, stridor, reduced peak expiratory flow, hypoxemia)
 - b. Reduced blood pressure (BP) or associated symptoms of end-organ dysfunction (e.g., hypotonia [collapse], syncope, incontinence)
2. Two or more of the following that occur rapidly after exposure to a likely allergen for that patient (minutes to several hours):
 - a. Involvement of the skin-mucosal tissue (e.g., generalized hives, itch-flush, swollen lipstongue-uvula)
 - b. Respiratory compromise (e.g., dyspnea, wheeze-bronchospasm, stridor, reduced peak expiratory flow, hypoxemia)
 - c. Reduced BP or associated symptoms of end-organ dysfunction (e.g., hypotonia [collapse], syncope, incontinence)
 - d. Persistent gastrointestinal symptoms (e.g., crampy abdominal pain, vomiting)
3. Reduced BP after exposure to known allergen for that patient (minutes to several hours):
 - a. Infants and children: low systolic BP (age-specific) or greater than 30% decrease in systolic BP. Low systolic BP for children is defined as less than 70 mmHg from 1 month to 1 year, less than (70 mmHg + [2 x age]) from 1 to 10 years, and less than 90 mmHg from 11 to 17 years.
 - b. Adults: systolic BP of less than 90 mmHg or greater than 30% decrease from that person's baseline

References

1. Lopes-Pacheco, M., et al., *Current understanding of the therapeutic benefits of mesenchymal stem cells in acute respiratory distress syndrome*. Cell biology and toxicology, 2019: p. 1-20.
2. Sun, P., et al., *Understanding of COVID-19 based on current evidence [published online ahead of print, 2020 Feb 25]*. Journal of Medical Virology, 2020.
3. *Clinical Pharmacology*. 2019, Elsevier: Tampa, FL.

1. INTRODUCTION

The purpose of this statistical analysis plan (SAP) is to describe the analyses to be included in the Clinical Study Report for Protocol HBCOVID02:

2. SUMMARY OF KEY PROTOCOL INFORMATION

2.1. Study Objective(s) and Endpoint(s)

Objectives	Endpoints
Primary Objective	Primary Endpoint

 To investigate the efficacy of HB-adMSCs in providing immune support against development of Coronavirus Disease by incidence of hospitalization for COVID-19, incidence of symptoms associated with COVID-19 (ie., fever, shortness of breath/difficulty breathing, and/or cough), and severity of COVID-19 associated symptoms (fever 38C or higher, cough, shortness of breath/difficulty breathing). 	
 Incidence of hospitalization for COVID-19. Incidence of symptoms associated with COVID-19
Secondary Objectives	Secondary Endpoints

 To investigate the efficacy of HB-adMSCs in the prevention of upper and lower respiratory infections in a high-risk population. 	
 Absence of upper/lower respiratory infections (with hospitalization criteria) up to 3 months post infusions. Change from baseline in leukocyte differential Change from baseline in C-Reactive Protein Change from baseline in TNF-alpha Change from baseline in IL-6 Change from baseline in IL-10 Clinically significant changes in laboratory values, vital signs, weight and physical examination results. Incidence of AEs (AEs) and serious AEs (SAEs) related to the drug

Protocol Number: HBCOVID02
 Hope Biosciences
 Statistical Analysis Plan

Confidential

Date: 14-Oct-2021
 Version: 1.0
 Status: Final

2.2. Study Design

Overview of Study Design and Key Features	
Randomized, double-blind, placebo-controlled, parallel group study	
Design Features	
 • Randomized, double-blind, Placebo controlled, parallel group study. • 53 Subjects • 4 Treatment groups 
 ▪ Group 1 → 2 x10⁸ cells (allogeneic HB-adMSCs 200MM) ▪ Group 2 → 1 x10⁸ cells (allogeneic HB-adMSCs 100MM) ▪ Group 3 → 5 x10⁷ cells (allogeneic HB-adMSCs 50MM) ▪ Group 4 → Placebo • Duration of treatment: up to 26 weeks, and overall study includes screening (up to 45 Days prior to randomisation), and 5 treatment visits after randomisation includes Infusion 1 (Week 0), Infusion 2 (Week 2), Infusion 3 (Week 6), Infusion 4 (Week 10) and Infusion 5 (Week 14). And follow up weeks of 18, 22 and end of study at Week 26.
Dosing	
 • Allogeneic HB-adMSCs is to be administered as an IV infusion. Each 10-mL syringe contains 5 x 10⁷ cells suspended in 5 mL of sterile saline to be diluted in 250 mL sterile saline.
Treatment Assignment	
 • Participants will be randomised 3:1 to receive HB-adMSCs treatments or Placebo.

2.3. Statistical Hypotheses

The null hypothesis for the primary endpoint of incidence of the hospitalizations due to COVID-19 symptoms at the end of the study is not different between the HB-adMSCs and Placebo treatment groups. The alternative hypothesis is that the treatments are different in the incidence of the hospitalizations due to COVID-19 at the end of the study. The hypothesis will be two-sided and tested at the 5% significance level.

The null hypothesis for the primary endpoint of incidence of the COVID-19 symptoms at the end of the study is not different between the HB-adMSCs and Placebo treatment groups. The alternative hypothesis is that the treatments are different in the incidence of the COVID-19 symptoms at the end of the study. The hypothesis will be two-sided and tested at the 5% significance level.

Additionally, a paired comparison will be made to compare the paired difference with placebo.

Protocol Number: HBCOVID02
Hope Biosciences
Statistical Analysis Plan

Confidential

Date: 14-Oct-2021
Version: 1.0
Status: Final

